4.10.3 Exploratory Efficacy Endpoints

Exploratory efficacy endpoints that are continuous rating scales recorded at multiple post-baseline visits (i.e., BAD Scale, Neuro-QOL, Euro-QOL, 25-foot walk test) will be evaluated using the MMRM approach described above for the primary efficacy endpoint. For endpoints obtained only at the baseline and final (Week 24) visits of the double-blind period (i.e., FIM/WeeFIM, DDK), the ANCOVA model will be used. The model will be run using the observed case (OC) procedure only. Summary statistics for efficacy measures will include graphical plots of mean and mean change from baseline values at each study visit during the double-blind period, by treatment group.

For analysis purposes, data from the pediatric and adult age groups will be pooled. All descriptive summary tables will be repeated using age group as a subgroup.

Treatment effects on categorical outcomes will be examined using frequency tables and tested using the Cochran-Mantel-Haenszel (CMH) chi-square methods with stratification by age group (pediatric, adult) ([Mantel and Haenszel, 1959](#)).

For the Interim Analysis, the Double-Blind FAS only will be used for analyses involving exploratory efficacy endpoints.

Statistical methods and estimation procedures are described below for each of the exploratory endpoints.

4.10.3.1 Clinician Global Impression of Improvement (CGI-I)

The CGI-I is measured on a 7-point scale, ranging from 1=very much improved to 7=very much worse since the start of treatment. Frequency tables will display the distribution of CGI ratings in each treatment group at Weeks 3, 6, 12, 18, and 24 of the double-blind treatment period. In addition, the percentages of patients who had a score indicating improvement, no change, or worsening, will be presented. This will be repeated using age group (pediatric, adult) as a subgroup.

The Cochran-Mantel-Haenszel test (CMH) row-mean score test (van Elteren test) will be used to evaluate the difference between treatment groups in average CGI-I ratings at each visit during the double-blind period, with stratification by age group (pediatric, adult).

A chi-squared test will be performed at Week 24 to determine treatment differences between the percentages of patients who had a score indicating improvement, no change, or worsening. Proportions, with estimated 95% CI, will be reported for each treatment group, along with a p-value corresponding to the treatment comparison.

A by-patient listing will be provided, which presents CGI-I scores across all assessments in the double-blind and open-label periods for patients in the Double-Blind FAS.

4.10.3.2 Barry Albright Dystonia (BAD) scale

The BAD scale assesses the signs of dystonia in 8 regions (eyes, mouth, neck, trunk, upper left/upper right extremities, and lower left/right extremities), each rated on a 5-point ordinal scale ranging from 0=absent to 4=severe. Thus, the total BAD score ranges from 0 to 32, with higher scores denoting greater severity of dystonia.

Frequency tables will display change from baseline for each of the 8 regions, as well as shift from baseline, by treatment group across each visit of the double-blind period, using categories for change from baseline region score (i.e., >0 , $=0$, <0 , ≤ -1 , ≤ -2 , ≤ -3), and categories for region score status (improvement, no change, or worsening).

Summary statistics will be presented for the total BAD score, including absolute and percent change from baseline, across each visit of the double-blind period. In addition, categories for change from baseline total BAD score (e.g., >0 , $=0$, <0 , ≤ -1 , ≤ -2 , ≤ -3 , ≤ -4), categories for percent improvement (i.e., decrease) in total BAD score from baseline (i.e., $<0\%$, $=0\%$, $>0\%$, $\geq 10\%$, $\geq 20\%$, $\geq 30\%$, $\geq 40\%$, $\geq 50\%$), and categories for total BAD score status (improvement, no change, or worsening) will be presented. These tables will be repeated using age group (pediatric, adult) as a subgroup.

Furthermore, a chi-squared test will be performed at each post-baseline assessment to determine treatment differences between the percentages of patients who had a total score indicating improvement, no change, or worsening. Proportions, with estimated 95% CI, will be reported for each treatment group, along with a p-value corresponding to the treatment comparison.

The treatment effect on change from baseline in total BAD score will be evaluated at Week 12 and the final (Week 24) visit using an MMRM, similar to the one described for the primary endpoint. The model will be run using the Double-Blind FAS.

Figures will be presented which show the total BAD score for each visit during the double-blind period, as well as change from baseline score, by treatment group.

A by-patient listing will be provided, which presents BAD scores (total and for each region) across all assessments in the double-blind and open-label periods for the Double-Blind FAS.

4.10.3.3 Quality of Life (QoL)

4.10.3.3.1 Neuro-QoL

The Neuro-QoL scale includes an upper extremity module (fine motor and activities of daily living) and a lower extremity module (mobility) with 19 items (20 items in the Pediatric Version).

Frequency tables will display change from baseline scores for each item of each module, including shift from baseline, by treatment group for Week 12 and Week 24. In addition, categories for change from baseline item score (i.e., <0 , $=0$, >0 , ≥ 1 , ≥ 2 , ≥ 3 , ≥ 4), and categories for item score status (improvement, no change, or worsening) will be presented. For these tables, data from the pediatric and adult versions will be presented in separate outputs.

For analytic purposes, responses across each module will be summed, and if necessary, rescaled, such that the total score will range from 0-100 for each module in both the Pediatric and Adult Versions. This methodology is described below.

For the Adult Version of the Neuro-QOL Upper Extremity module, in which there are 20 items with each response ranging from 1-5, the total score is computed via summation, and no rescaling is necessary. In the Adult Version of the Neuro-QOL Lower Extremity module, there are 19 items with each response ranging from 1-5. The total score is thus computed by summing the responses across the 19 items, and then multiplying this sum by (20 / 19).

In each of the Pediatric Version of the Neuro-QOL Upper and Lower Extremity modules, there are 20 items with each response ranging from 0-4. For all items, each response is rescaled to correspond to a 1-5 scale, and then summed to produce the total score.

Within each Neuro-QOL module, the rescaled total scores from the adult and pediatric versions of the assessment will be pooled. Descriptive statistics of the rescaled total score for each of the Neuro-QOL modules, as well as absolute and percent change from baseline, will be presented for patients in the Double-Blind FAS at each post-baseline assessment during the double-blind period. In addition, categories for change from baseline rescaled total score (e.g., <0 , $=0$, >0 , ≥ 1 , ≥ 2 , ≥ 3 , ≥ 4), categories for percent

improvement (i.e. increase) in rescaled total score from baseline (i.e., <0%, =0% >0%, $\geq 10\%$, $\geq 20\%$, $\geq 30\%$, $\geq 40\%$, $\geq 50\%$), categories for rescaled total score status (improvement, no change, or worsening) will be presented for each module. This table will be repeated using age group (pediatric, adult) as a subgroup.

Chi-squared tests will be performed for each module at each post-baseline assessment to determine treatment differences between the percentages of patients who had a re-scaled total score indicating improvement, no change, or worsening. Proportions, with estimated 95% CI, will be reported for each treatment group, along with a p-value corresponding to the treatment comparison.

In addition, the change in Neuro-QoL assessments (rescaled score for each module) from baseline to the Week 12 and final (Week 24) visit will be evaluated at each time point using an MMRM, similar to the one described for the primary endpoint. The model will be run using the Double-Blind FAS.

A by-patient listing will be provided, which presents the raw responses to all items in the Neuro-QOL assessment, along with the rescaled total score for each module, across all assessments in the double-blind and open-label periods for patients in the Double-Blind FAS.

4.10.3.3.2 Euro-Qol

The EQ-5D-3L (for adult patients) measures 5 dimensions (mobility, self-care, usual activities, pain/discomfort and anxiety/depression), each rated at 3 levels: 1=no problems, 2=some problems, 3=extreme problems. The scale also records the patient's self-rated health on a visual analogue scale (VAS) from 0=the worst health you can imagine, to 100=the best health you can imagine. The EQ5DY (for pediatric patients) measures the same 5 dimensions on a similar 3-point scale and uses the same VAS for the patient to self-rate health.

Frequency counts of the change from baseline score across each of the 5 dimensions, as well as shift from baseline, will be presented for each visit during the double-blind period. Categories for change from baseline dimension score (i.e., >0 , $=0$, <0 , ≤ -1), and categories for dimension score status (improvement, no change, or worsening) will be presented at Week 24, as well. These tables will be repeated using age group (pediatric, adult) as a subgroup.

Furthermore, each patient's 5-digit EQ-5D state will be transformed into a single EQ-5DTM index score by following the algorithm, or value set, specified for his or her relevant country. These value sets are derived based off surveys conducted in representative samples of the given countries. The value set is anchored at 0=dead and 1=full health. The EURO-QOL group provides the value set for performing these calculations, and one such reference table can be found in [Janssen \(2014\)](#). If there are any

missing data across the 5 dimensions at a given visit, then the index score cannot be validly calculated and is considered missing.

Descriptive statistics of the EQ-5D™ index score will be presented for patients in the Double-Blind FAS at each visit of the double blind period, including absolute change from baseline. Categories for percent improvement (i.e., increase) in EQ-5D™ index score from baseline (i.e., <0%, =0% >0%, ≥10%, ≥20%, ≥30%, ≥40%, ≥50%), and categories EQ-5D™ index score status (improvement, no change, or worsening) will be presented. In addition, descriptive statistics of the patient's self-rated health on the VAS, as well as absolute change from baseline, will be presented for each visit of the double-blind period. This table will be repeated using age group (pediatric, adult) as a subgroup.

A chi-squared test will be performed at each post-baseline assessment to determine treatment differences between the percentages of patients who had an EQ-5D™ index score indicating improvement, no change, or worsening. Proportions, with estimated 95% CI, will be reported for each treatment group, along with a p-value corresponding to the treatment comparison.

Furthermore, the change in each Euro-QoL assessment (EQ-5D™ index score, and the EQ VAS) from baseline to the Week 12 and final (Week 24) visit will be evaluated using an MMRM, similar to the one described for the primary endpoint. The models will be run using the Double-Blind FAS.

A by-patient listing will be provided, which presents Euro-QOL scores (score on 5 dimensions, EQ-5D™ index score, and VAS score) across all assessments in the double-blind and open-label periods for patients in the Double-Blind FAS.

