4.10.1 Primary Efficacy Endpoint

The PKAN-ADL consists of 12 items related to activities of daily living, including eating, dressing, and walking. Each item has responses ranging from 0-4, with a higher value indicating greater disability in the given activity. To compute the total score, responses are summed across the 12 items.

For analysis purposes, data from the pediatric and adult age groups will be pooled. All descriptive summary tables will be repeated using age group as a subgroup.

Descriptive statistics will be presented for the PKAN-ADL total score, with absolute and percent change from baseline, by treatment group for each visit of the double-blind

period. For post-baseline assessments, categories for change from baseline total score (e.g., >0 , $=0$, <0 , ≤ -1 , ≤ -2 , ≤ -3 , ≤ -4), categories for percent improvement (i.e., decrease) in total score from baseline (i.e., $<0\%$, $=0\%$, $>0\%$, $\geq 10\%$, $\geq 20\%$, $\geq 30\%$, $\geq 40\%$, $\geq 50\%$), and categories for total score status (improvement, no change, or worsening) will be presented. These categories may be adjusted in a way that ensures that the categories contain at least 10% of patients. This will be run using the Double-Blind FAS, and repeated using the PPS, as a sensitivity analysis.

Change from baseline will be calculated by subtracting the baseline total score from the post baseline total score. Percent change from baseline will be calculated as:

$$100 * (\text{Observed Score at Post-Baseline Visit} - \text{Observed Score at Baseline}) / \text{Observed Score at Baseline}$$

Furthermore, a chi-squared test will be performed at each post-baseline visit to determine treatment differences between the percentages of patients who had a total score indicating improvement, no change, or worsening. Proportions, with estimated 95% CI, will be reported for each treatment group, along with a p-value corresponding to the treatment comparison.

Frequency tables will display change from baseline for each of the 12 items, as well as shift from baseline, by treatment group for each post-baseline assessment of the double-blind period. In addition, categories for change from baseline item score (i.e., >0 , $=0$, <0 , ≤ -1 , ≤ -2 , ≤ -3), and categories for item score status (improvement, no change, or worsening) will be presented. These summaries will be run using the Double-Blind FAS and repeated using the PPS, as a sensitivity analysis.

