4.10.3.5 Function Measures

Ambulation: Patients able to attempt this assessment will have 2 trials to walk 25 feet, and the average time (in seconds) of these trials will be taken. Patients must successfully complete 2 trials in order for the assessment to have been considered completed. If there is only data available for 1 trial, for reasons other than a patient's inability to perform the test, then the time for the single, available trial will be considered as the average.

Descriptive statistics will be used to summarize average walking speeds (in seconds) at each study visit of the double-blind treatment period (Baseline, Weeks 6, 12, 18, and 24) for patients in the Double-Blind FAS, along with absolute and percent change from baseline for post-baseline visits. Categories for percent improvement (i.e., decrease) in average walking speed (in seconds) from baseline (i.e., $<0\%$, $=0\%$, $>0\%$, $\geq 10\%$, $\geq 20\%$, $\geq 30\%$, $\geq 40\%$, $\geq 50\%$), and categories for average walking speed (improvement, no change, or worsening) will be presented, as well. This table will be repeated using age group (pediatric, adult) as a subgroup.

Moreover, the walking speeds will be converted to z-scores, using the baseline values of patients in the Double-Blind FAS as reference values. The z-score conversion will follow the below formula:

(Observed value [in seconds] – average of all baseline values [in seconds]) / standard deviation of all baseline values [in seconds].

Then, the z-score will be adjusted (multiply z-score by -1) so that a higher z-score will correspond to a better speed (fewer seconds). For patients who are unable to complete the 25-foot walk test, a z-score will be imputed using the worst observed z-score across all patient visits.

Descriptive statistics of the z-score, including absolute and percent change from baseline, will be presented for patients in the Double-Blind FAS at each visit during the double-blind period. Depending on the number of patients with available data, the MMRM model (as described for the primary endpoint) will be used to evaluate the treatment effect on change from baseline walking speed z-score. The difference between adjusted treatment means will be reported, together with its 95% CI.

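### The SAP plans percent change for a walk-test z-score centred on zero, where the statistic has no consistent direction; percent bands for the EQ-5D index are a lesser, optional point

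*SAP*

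**What the plan says.** **Walk test (SAP 4.10.3.5).** Average times in seconds are summarised with absolute and percent change, percent-improvement bands, and improvement/no change/worsening categories. Times are also converted to z-scores, "using the baseline values of patients in the Double-Blind FAS as reference values": the baseline mean is subtracted and the result is divided by the baseline SD. The sign is then reversed: "Then, the z-score will be adjusted (multiply z-score by -1) so that a higher z-score will correspond to a better speed". Patients who cannot complete the test receive the worst z-score observed at any visit. For the z-score the SAP plans "Descriptive statistics of the z-score, including absolute and percent change from baseline". The model, if enough data are available, is an MMRM on change in z.

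**Formula (SAP 4.10.1).** The passage that begins "Percent change from baseline will be calculated as" gives 100 × (post-baseline − baseline) / baseline for the PKAN-ADL. No other percent-change formula appears in the SAP, and no rule covers a zero or negative baseline.

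**EQ-5D index (SAP 4.10.3.3.2).** On the scale, the SAP says: "The value set is anchored at 0=dead and 1=full health". No minimum is stated. Descriptive statistics are planned "at each visit of the double blind period, including absolute change from baseline". Percent enters only through the bands ("Categories for percent improvement (i.e., increase) in EQ-5D"), which run from below 0% to 50% or more.

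**Status (SAP 4.10.4).** Endpoints other than the primary and secondary are exploratory.

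**The concern.** A percent change needs a scale whose zero means none of the quantity. Walking time in seconds has such a zero. The z-score does not: its zero is the average baseline time of the patients who happened to be enrolled. Dividing by a patient's distance from that average produces a figure whose sign depends on which side of the average the patient started.

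At stake is the readability of a table in the interim clinical study report. A mean or median of these values could fall below zero when every patient walked faster, or rise when patients slowed down. The arms could also differ only because their patients were placed differently around the mean at baseline.

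**Working it through.** The plan gives no figure of its own to reproduce here, so the check applies its formulas.

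**Step 1. Percent change of z in terms of seconds.** Let m and SD be the baseline mean and SD, s0 the patient's baseline time and s1 the later time. Then z = −(s − m)/SD = (m − s)/SD. The average of z over the observed baselines is 0, so unless all times are equal, some baselines are negative. Using the formula from Section 4.10.1:

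100 × (z1 − z0)/z0 = 100 × (s0 − s1)/(m − s0)

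The SD cancels. The denominator is the distance from the sample mean, and it is negative for anyone slower than m.

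**Step 2. Direction.**
- Improvement from −0.50 to −0.25: 100 × 0.25/(−0.50) = −50%.
- Deterioration from −0.50 to −0.75: 100 × (−0.25)/(−0.50) = +50%.

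**Step 3. The same gain for everyone.** Assume m = 12 s and SD = 6 s (neither is in the documents), and let each of seven illustrative patients become 1 s faster. Absolute change in z is 1/6 = +0.167 for all of them.

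| Baseline → later (s) | Percent change in seconds | Baseline z | Percent change in z |
|---|---|---|---|
| 6 → 5 | −16.7 | 1.000 | +16.7 |
| 9 → 8 | −11.1 | 0.500 | +33.3 |
| 11.5 → 10.5 | −8.7 | 0.083 | +200 |
| 12.5 → 11.5 | −8.0 | −0.083 | −200 |
| 15 → 14 | −6.7 | −0.500 | −33.3 |
| 18 → 17 | −5.6 | −1.000 | −16.7 |
| 24 → 23 | −4.2 | −2.000 | −8.3 |

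The first six z percentages sum to zero, so the mean is −8.3/7 = −1.2%. The median is −8.3%. All seven patients improved.

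**Step 4. How many patients are affected.** The share slower than the mean, and so with reversed sign, depends on the distribution of times, which is an assumption:
- normal: 50%;
- lognormal with coefficient of variation 0.3, 0.5 or 1.0: 44%, 41% or 34%.

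About 8% to 9% have |z| below 0.1 in these cases. Under normality about 20% have |z| below 0.25 (probability 0.197), and for them a change of 0.25 SD exceeds 100%.

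**Step 5. The imputation rule.** The worst observed z is negative. If it were −2.0 (assumed), a patient at −0.5 who becomes unable to complete the test would score 100 × (−2.0 + 0.5)/(−0.5) = +300%.

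**Step 6. EQ-5D index (secondary).** If the same formula is used:
- a gain of 0.05 is 100% from a baseline of 0.05 and 10% from 0.50;
- a gain of 0.10 is 12.5% from 0.80, 20% from 0.50, 50% from 0.20 and 200% from 0.05.

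Only if a country value set gives values below zero does the sign reverse: a gain of 0.10 from −0.20 would be 100 × 0.10/(−0.20) = −50%, in the lowest band.

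**The case against.** **The formula is given only for the PKAN-ADL.** This is correct, so carrying it over to the z-score is an inference. A programmer could divide by the absolute baseline instead. That restores the sign but not the meaning: in Step 3 the 12.5 s patient becomes +200% and the 24 s patient +8.3% for the same one-second gain. The objection changes which defect appears and does not remove the problem.

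**Tables would label improving walkers as worsening.** A reader might infer this, and the documents do not support it. The percent bands and the status categories in Section 4.10.3.5 are defined on time in seconds, where they behave properly. For z the plan has only summary statistics of percent change, so a faster walker could contribute a negative number but would not receive a worsening label.

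**The EQ-5D bands reverse sign.** A reader might infer this too. It requires index values below zero. The SAP fixes zero at death and states no minimum, so negative values are neither stated nor excluded. What follows without that assumption is ordinary small-denominator instability, to which the percent bands for the PKAN-ADL, UPDRS Part III and BAD are also open in principle. It is a reason to prefer absolute bands, not an error in the plan.

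**Nothing inferential depends on it.** This stands in full. The MMRMs use change from baseline, the EQ-5D chi-squared test uses status categories, and absolute change is already planned for both measures.

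**Conclusion.** The z-score point holds. Percent change of a sign-reversed z-score centred on the sample's own baseline mean has no interpretable direction. That some baselines are negative follows from the SAP's definition alone. The reversed sign rests on applying the PKAN-ADL formula. The 34% to 50% range rests on the assumed distributions in Step 4.

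The EQ-5D index point is secondary: the bands are unstable at small baselines, and sign reversal remains conditional on value sets that the documents do not show.

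The effect is small. It is confined to exploratory descriptive output, and the primary and secondary analyses are untouched.

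**What to change.** In SAP Section 4.10.3.5, remove percent change from the descriptive statistics planned for the z-score. Keep absolute change in z, and keep the percent change and percent bands already planned in seconds. This deletes one phrase and the matching table rows. It needs no new data and alters no model.

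Optionally, in Section 4.10.3.3.2, replace the percent bands for the EQ-5D index with absolute-change bands, as the SAP already has for the BAD, Neuro-QoL and FIM totals. This costs slightly more, because cut-points suited to the index scale must be chosen and written down before unblinding.
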